## Appendix B METHODS OF CLINICAL EVALUATIONS

Any changes to the procedures described in this appendix will be provided under separate cover. Study procedures performed during the COVID-19 pandemic will be conducted in accordance with medical guidance to reduce risk of COVID-19 transmission between study staff and subjects (available at [www.ao.org/covid-19](http://www.ao.org/covid-19)). It is recommended Investigators periodically revisit the [ao.org/covid-19](http://ao.org/covid-19) website to identify and implement any updated recommendations made by AAO. Local, state, and federal public health guidance also will be followed, and it is recommended these guidances also be visited once a month to see if they have changed.

### 1.0 MANIFEST SUBJECTIVE REFRACTION (WITHOUT CYCLOPLEGIC EYE DROPS)

It is essential that a consistent and standard procedure be used to obtain manifest refraction measurements. The measurements will be obtained by a qualified ophthalmologist, optometrist or trained ophthalmic technician using a phoropter or trial frame with loose lenses, in 0.25 D steps, in a calibrated refraction lane. The principal of maximum plus prescription while maintaining optimum visual acuity (not just darker letters) should be adhered to. At no time during the study will autorefraction be utilized as a final endpoint refraction. Autorefractor or lensometer readings may only be utilized to obtain a starting point for the refraction, if necessary.

To ensure consistency, all refractions will be performed at an optical distance of 4 meters using the M&S Clinical Trial Suite. This refraction will be considered the “unadjusted manifest refraction at 4 m”. The “adjusted manifest refraction” is the “unadjusted manifest refraction “ minus 0.25 D used to correct for optical infinity at 4 m. Both “adjusted” and “unadjusted” manifest refraction values will be recorded on source documentation, but only the adjusted value will entered as eCRF data. Note that the “**adjusted manifest refraction**” (“**unadjusted manifest refraction**” at 4 meters minus 0.25 D) is the value that is used for DCIVA and DCNVA measurements.

#### 1.1 Preoperative Manifest Subjective Refraction

If the subject has a current pair of glasses for distance vision, they can be measured with a lensometer and these measurements used as the beginning approximate refraction. If the subject does not have glasses for distance vision, retinoscopy or autorefraction may be performed by an examiner proficient in this procedure as the beginning approximate refraction. If the subject is a contact lens wearer, they should be advised to arrive for the preoperative testing wearing spectacles and not their contact lenses.

**AUTOREFRACTION ALONE IS NOT ALLOWED AT ANY POINT IN THIS STUDY.  
RESULTS MUST BE REFINED USING SUBJECTIVE TECHNIQUES.**

The manifest subjective refraction at 4 meters MUST be transferred to the trial frame for BCDVA testing. If for any reason (e.g., dense cataract) manifest refraction cannot be obtained, the results should be documented as not done (ND) and not entered as zeros. In the event of

this occurrence, BCDVA will not be tested and the reason for ND will be required in the source document and eCRF.

Contact lens wearers must demonstrate a stable refraction (within  $\pm 0.50$  D for both sphere and cylinder) on two consecutive exam dates. Stability of the refraction is determined under the following conditions:

- Lenses are not worn for at least 1 week (rigid contact lenses) or 3 days (soft contact lenses) prior to the first refraction used to establish stability and through the day of surgery;
- The two refractions are performed at least 7 days apart.

## 1.2 Postoperative Manifest Subjective Refraction

The subject should be refracted using the same method and procedure as described in Section 1.1 of this appendix.

## 2.0 VISUAL ACUITY TESTING

It is essential that a standard procedure be used to obtain visual acuity (VA) measurements. The VA measurements should be obtained by a qualified ophthalmologist, optometrist or trained ophthalmic technician using the Clinical Trial Suite (M&S Technologies, Niles, IL) hardware and software that will be supplied by the Sponsor. Training on the use of Clinical Trial Suite instrumentation will be conducted and documented by a qualified representative of M&S Technologies prior to its use with enrolled subjects. VA testing will be performed by masked study personnel using a trial frame.

Visual Acuity Testing for all subjects:

- Best-corrected distance visual acuity (BCDVA) will be measured at distance of 4 meters with the manifest refraction obtained at 4 meters (**Unadjusted** Manifest Refraction)
- Uncorrected distance visual acuity (UCDVA) will be measured at distance of 4 meters with a +0.25D lens to adjust for optical infinity
- Distance corrected intermediate visual acuity (DCIVA) will be measured at distance(s) specified in [Appendix A](#) with the “adjusted manifest refraction”, which is the manifest refraction obtained at 4 meters minus 0.25 D to obtain the optical infinity manifest refraction (**Adjusted** Manifest Refraction)
- Uncorrected intermediate visual acuity (UCIVA) will be measured with Phase II and Phase III subjects at distance(s) specified in [Appendix A](#) at 66 cm with no corrective lens
- Distance corrected near visual acuity (DCNVA) will be measured at distance(s) specified in [Appendix A](#) with the “adjusted manifest refraction”, which is the manifest refraction obtained at 4 meters minus 0.25 D (**Adjusted** Manifest Refraction).
- Uncorrected near visual acuity (UCNVA) will be measured at distance(s) specified in [Appendix A](#) with no corrective lens

## 2.1 Description and Testing Methodology

The Clinical Trial Suite is a computerized vision testing system consisting of a computer tablet and frame to hold the tablet that allows it to be stationed at different distances from a seated

subject. The tablet frame also has lights attached to it that allow vision testing to be conducted with or without glare. The frame can be moved so that near, intermediate, or far VA can be determined, with the ETDRS optotype display adjusted for distance from subject to display to accommodate the effect of distance of the size of the ETDRS letters. The Clinical Trial Suite will use high contrast ETDRS letters and randomize the letter display during every use to eliminate any effect of memorization bias. The distance from subject to display for near, intermediate, and far distance VA testing will be standardized for all clinical sites and for all subjects.

The chart display on the tablet should be at a comfortable viewing angle for the subject, approximately head high. The subject should attempt to read each letter, line by line, left to right, beginning with line 1 at the top of the chart. The subject should be told that the chart has letters only, no numbers. The subject should be asked to read slowly, about 1 letter per second, so as to achieve the best identification of each letter. Subjects should be instructed not to squint, and the tester should closely watch the subject during testing and warn him/her if squinting is observed. The subject is not to proceed to the next letter until a definite response is given.

If the subject changes a response (e.g., “that was a ‘C’ not an ‘O’) before the next letter has been read aloud, then the change must be accepted. If the subject changes a response having read the next letter, then the change is not to be accepted. The examiner should never point to the chart or to specific letters on the chart during the test. A maximum effort should be made to identify each letter on the chart. This may include encouraging the subject to guess. If the subject identified a letter as 1 of 2 letters, he or she should be asked to choose 1 letter and, if necessary, to guess. When it becomes evident that no further meaningful readings can be made, despite encouragement to read or guess, the examiner should stop the test for that eye and those testing conditions. However, all letters on the last line should be attempted as letter difficulties vary and the last letter may be the only one read correctly. The number of letters missed or read incorrectly should be noted. In order to provide standardized and well controlled assessments of visual acuity during the study, all visual acuity assessments at a single site must be consistently done using the same lighting conditions during the entire study.

## **2.2 Room Illumination**

Standard lighting conditions to be used in VA testing are Photopic:  $85 (\pm 2) \text{ cd/m}^2$  and Mesopic:  $3 (\pm 0.5) \text{ cd/m}^2$ . If an Investigator is unable to use these lighting conditions or has lighting conditions that vary slightly from these target illuminations, they should discuss their current lighting conditions with the Sponsor.

## **2.3 Subject Instructions**

Subjects will be instructed that their vision will be tested at different distances, sometimes with the room lights on and sometimes with the room lights off. They will be asked to sit quietly during testing, with no head movements relative to the chart display allowed. If subjects need one or more brief breaks from the testing, this will be allowed.

## **2.4 Visual Acuity Assessments**

See Appendix A for schedule of VA assessments. VA assessments should be done only once per visit for each eye (or subject, in the case of binocular VA), distance to eye chart, and lighting condition.

## **3.0 SLIT LAMP EXAM**

Slit lamp examination will be performed using a slit lamp biomicroscope and observations graded per the following classification:

### **Cataract Type**

- Nuclear
- Cortical
- Posterior sub-capsular
- Combination

### **Cataract Density**

- 1+ = Slight
- 2+ = Moderate
- 3+ = Dense
- 4+ = Very dense

**Lids** – Normal / Abnormal+

**Iris/Pupil** – Normal / Abnormal+

**Conjunctiva** – Normal / Abnormal+

+Abnormal is defined as beyond the normal range encountered in healthy individuals of a similar age

Hyperemia

- 0 None
- 1 Mild
- 2 Moderate
- 3 Severe
- 4 Very Severe

**Cornea**

Superficial Punctate Keratitis

- 0 None
- 1 Mild
- 2 Moderate
- 3 Severe
- 4 Very Severe

Corneal Wound Edema (postoperative only)

- 0 None
- 1 Mild
- 2 Moderate
- 3 Severe

Corneal Stromal Edema (preoperative and postoperative)

- 0 None      No evidence of corneal swelling with normal transparency
- 1 Mild      Mild corneal swelling
- 2 Moderate      Moderate corneal swelling
- 3 Severe      Definite widespread cloudiness or haziness giving dull ground glass appearance to cornea, or numerous coalescent bullae

The slit lamp examination includes the measurement of aqueous cell and flare by the SUN Working Group grading system. For the evaluation of cells and flare, using a 1 mm x 1 mm slit beam, the following SUN grading scheme will be used:

### **Anterior Chamber Cells**

Grade	Cells in Field
0	<1
0.5+	1-5
1+	6-15
2+	16-25
3+	26-50
4+	>50

### **Anterior Chamber Flare**

Grade	Description
0	None
1+	Faint
2+	Moderate
3+	Marked
4+	Intense

### **Posterior Capsular Haze**

Assessment of the severity of any PCO will be done with pupil dilation at the slit lamp using the following grading scale:

Grade 0 – None	No growth is seen on any portion of the visible lens capsule.
Grade 1 – Trace or Mild	Lens epithelial cells can be seen in the periphery where the anterior capsule has retracted from the front of the IOL and is now interacting with the posterior capsule, but there are very few central cells.
Grade 2 – Moderate	The peripheral cells have become much denser and are starting to invade the central area.
Grade 3 – Severe	The lens epithelial cells have met one another in the middle and are forming a sheet over the posterior capsule.

## **4.0 INTRAOCULAR PRESSURE (IOP)**

IOP measurements will be obtained using a calibrated Goldmann Type Applanation Tonometer in accordance with manufacturer's instructions.

## **5.0 PUPIL SIZE**

Pupil size will be measured with a pupillometer at the corneal plane to the nearest 0.1 mm. Eye illumination for pupil measurement will be identical to the photopic and mesopic illumination used for visual acuity testing – 85 ( $\pm$  2) cd/m^2 and 3 ( $\pm$  0.5) cd/m^2, respectively. Pupil measurement will be initiated only after the eye has had time to fully adapt to the testing conditions (approximately 10 minutes).

## **6.0 DILATED FUNDUS EXAM**

Using an Ophthalmoscope, light is shone into the eye and the retina and the optic nerve are examined. This exam is used to evaluate the internal structures of the eye. The Investigator will classify the fundus as “normal” or “abnormal.” If abnormal, the investigator will describe the abnormality. The investigator will also rate the clarity of fundus visualization as “adequate” or “inadequate”.

## 7.0 OCT IMAGING

Approximately 20 Group 1 subjects and 10 Group 2 subjects will participate in OCT imaging at 2-3 clinical sites having similar or identical OCT equipment. For sites and subjects participating in OCT imaging, images of first implanted eye will be taken. OCT images will be obtained after the dilated exam, and eyes found to have any abnormality of the visual axis or retinal structures will be excluded from the imaging sub-study. For each first implanted eye, three images of the macula and three images of the optic nerve will be obtained by qualified site personnel, labeled with the Subject ID number, and submitted to the Sponsor (or designee) for assessment. The image quality will be assessed to determine adequacy for visualization of retinal structures, with the results rated on the following scale:

- 0 = Ungradable (including failure to visualize the macula or optic nerve)
- 1 = Poor quality image
- 2 = Fair quality image
- 3 = Good quality image
- 4 = Excellent quality image

If difficulty with visualization is encountered during the process of obtaining OCT images, conventional fundus photographs will be taken.

## 8.0 TRIAL FRAME ASTIGMATISM SIMULATION

Participating subjects should have the following characteristics (in both eyes) upon having consented to the Trial Frame Astigmatism Simulation sub-study:

1. Signed consent (no later than Visit 5) to participate in the sub-study
2. Completed visit 5
3. Have a best-corrected distance visual acuity of 20/25 or better as noted in each eye at Visit 5
4. Subjects should not have corneal edema, increased IOP or any AE / SAE at Visit 5, as per the reportable AEs/ SAEs clarified in section 12.4.1 of the protocol.
5. In addition, subjects must be willing to complete their participation on the Trial Frame sub-study between 2 and 30 days after completion of Visit 5.
6. Subjects with oblique post-operative residual astigmatism (axis between 30 to 60 degrees or 120 to 150 degrees) will be excluded from participation in the sub-study.

Enrollment will be sequential with consecutive subjects enrolled onto the Trial Frame astigmatism simulation sub-study at each site in order of their completion of post-operative Visit 5 and based on their eligibility. The subject will provide consent for the Trial Frame astigmatism simulation sub-study by completion of Visit 5 and return at Visit 6 to undergo the trial frame evaluation to assess distance-corrected visual acuities with various amounts of astigmatism. Eligibility for the sub-study will be confirmed by the completion of Visit 5 and

subjects will be enrolled in it when the Informed Consent document is signed. Visit 6 will include review/update of concomitant medications, adverse events, and measurement of monocular distance corrected visual acuity for far (4 m), intermediate (66 cm), and near (40 cm) distance under photopic conditions with varying degrees of simulated residual astigmatism with 2.00 D, 1.5 D, and 1.0 D CYL. Participants in the sub-study will be seen at only one visit (Visit 6) for the trial frame evaluation which will complete their participation in the study. Assessments are shown in the Study Flow Chart in [Appendix A](#).

The below assessments will be recorded:

- i. For the (4-meter) manifest-corrected distance (4 m) testing:
  - Visual acuity will be assessed without astigmatic blur; and
  - With astigmatic blur for each astigmatic condition (power/axis orientation);
- ii. For the distance corrected intermediate (66 cm) testing :
  - Visual acuity will be assessed without astigmatic blur; and
  - With astigmatic blur for each astigmatic condition (power/axis orientation)
- iii. For the distance corrected near (40 cm) testing:
  - Visual acuity will be assessed without astigmatic blur; and
  - With astigmatic blur for each astigmatic condition (power/axis orientation)

The order of testing will follow the A and B Eye pre-operative assignments relating to the order of surgical implantation of the IOL and each eye of the subject will be tested for each distance and astigmatic condition, followed by a repeat of the same testing with the other eye.

The purpose of the Trial Frame astigmatism sub-study is to evaluate the effect of simulated residual astigmatism on distance, intermediate, and near visual acuities in eyes implanted with the enVista trifocal toric intraocular lenses (IOLs).

The trial frame evaluation will assess distance-corrected visual acuities with various amounts of additional astigmatism at distance / far, intermediate, and near distances, in that order, for each eye of each subject monocularly. ETDRS charts appropriate for each distance will be used in measuring visual acuity for the various cylinder power conditions. Each eye of the participating subjects will be evaluated monocularly, beginning with the subject's A eye (Right/ Left) and repeating for the subject's B eye (Left/ Right).

The Trial Frame is placed on the subject and adjusted to sit comfortably on the subject's face. The subject's eyes are centered relative to the lens wells of the frame via adjustments to the temple length, to the nose pad for frame height , pantoscopic tilt and leveling of the frame and the interpupillary distance.

The subject's distance-corrected refraction and testing will begin at far distance (4 m) using the Clinical Trial Suite system (M&S Technologies, Niles, IL) with no additional cylinder trial lens in the trial frame for measurement of monocular distance corrected visual acuity for each eye. The distance correction used in the trial frame for testing at far distance (4 m) is the

**unadjusted** manifest refraction performed at 4 m; however, the distance correction used in the trial frame for testing at intermediate (66 cm) and near (40 cm) distances is the **adjusted** manifest refraction (i.e., the manifest refraction at 4 m adjusted by adding an additional -0.25 D). See [Table 4](#) below.

In order to ensure the spherical equivalent is kept at a constant, the examiner must modify the spherical power with each plus cylinder power added to the trial frame. This procedure is necessary to avoid increasing the spherical equivalence and blurring the vision with induced Hyperopia.

For example, when adding a residual plus cylinder power of 1.0D to the Trial Frame, 0.5D of spherical power must be subtracted to ensure spherical equivalence is maintained at a constant. The following examples demonstrate the proper subtraction of spherical power with the addition of each cylindrical power to maintain a constant spherical equivalent compared to the manifest refraction.

Examples

- 1) -0.75 sph should be placed in the trial frame with the +1.50 cylinder,
- 2) -0.50 sph should be placed in the trial frame with the +1.00 cylinder,
- 3) -1.00 sph should be placed in the trial frame with the +2.00 cylinder.

Residual astigmatism then will be optically simulated for each subject at distance / far (4 m), intermediate (66 cm), and near (40 cm) distances (in that order) using additional plus cylinder trial lenses placed at the 180° axis (i.e., simulating ATR astigmatism) and then at the 90° axis (i.e., simulating WTR astigmatism). The order of trial lenses to be used with a subject will be the 2.00 D plus cylinder lens (placed first at 180° and then at 90°) followed successively by use of the 1.50 D plus cylinder lens (placed first at 180° and then at 90°) and then the 1.00 D plus cylinder lens (placed first at 180° and then at 90°). The A eye will be measured first, using the various cylinder lenses for distance / far, intermediate, and near distances. The same order will then be repeated for the B eye.

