### 13.5.5.4 Trial Frame Astigmatism Simulation

The following will be summarized by treatment group using the sample size, mean, standard deviation, minimum, first through third quartiles, and maximum.

- logMAR VA for each assess combination of distance (40 cm, 66 cm, 4 m), cylinder power (0 D, +1.00 D, +1.50 D, +2.00 D) and axis (90 degrees, 180 degrees)
- The within-eye difference in logMAR VA between without astigmatic correction (0.00 D cylinder power) and with astigmatic correction, for each combination of distance, non-zero cylinder power, and axis

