4.2.4 Trial Frame Astigmatism Simulation

Approximately 30 Group 1 subjects and 15 Group 2 subjects will participate in the trial frame astigmatism sub-study at up to 10 clinical sites. A total of 50 subjects will be enrolled in the sub-study to allow for a 10% loss. Enrollment will be sequential with consecutive subjects enrolled onto the Trial Frame astigmatism simulation sub-study at each site in order of their completion of Post-Operative Visit 5 (Day 330 to 420 after second eye IOL implantation) and based on their eligibility. The purpose of the Trial Frame Astigmatism Simulation sub-study is to evaluate the effect of simulated residual astigmatism on distance, intermediate, and near visual acuities in eyes implanted with the enVista trifocal toric IOLs.

5 Treatment Plan

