14.2 Manifest Refraction

Prior to analysis, categorization, and presentation, refraction results will be converted to negative cylinder notation by application of the following steps in order.

1. If the cylinder is missing, then the negative cylinder notation sphere, cylinder, and axis will all be missing.
2. If the non-missing cylinder is less than or equal to zero, then the refraction results are already in negative cylinder notation and will not be changed.

3. If the cylinder is greater than zero, then the following steps will be completed
 - a. The sphere in negative cylinder notation will equal the sum of the positive cylinder notation sphere and cylinder.
 - i. However, if the positive notation sphere is missing then the negative cylinder notation sphere will also be missing.
 - b. The negative cylinder notation cylinder will equal the negative of the positive cylinder notation cylinder
 - c. The negative cylinder notation axis will equal the positive cylinder notation axis rotated by 90 degrees, with necessary adjustments to ensure that the resulting axis is within the interval from 1 to 180 degrees, inclusive.
 - i. If the positive cylinder notation axis is missing, then the negative axis notation cylinder will also be missing.

Summaries will be by treatment received and visit for the Modified Safety Set for first eyes, second eyes, and all eyes separately.

Sphere (D), cylinder (D), and spherical equivalent (D) will be summarized using continuous summary statistics. In addition, proportion of eyes with difference between intended spherical equivalent and achieved spherical equivalent within +/- 0.50 D and within +/- 1.00 D will be summarized using categorical statistics.

Axis will be summarized using continuous and categorical (none, with-the-rule, oblique, against-the-rule) summary statistics using the following definitions.

- None: 0°
- With-the-rule: 1° to 30° or 150° to 180°
- Oblique: 31° to 59° or 121° to 149°
- Against-the-rule: 60° to 120°

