14.12 Trial Frame Astigmatism Simulation Sub-Study Assessments

The following trial frame astigmatism simulation sub-study assessments will be conducted at Post Operative Visit 6 (Day 2 to 30 after Visit 5):

- BCDVA photopic monocular (no additional sphere, cylinder, or axis)
- BCDVA photopic monocular (simulated astigmatism +2.00 D plus cylinder, 180 $^{\circ}$)
- BCDVA photopic monocular (simulated astigmatism +2.00 D plus cylinder, 90 $^{\circ}$)
- BCDVA photopic monocular (simulated astigmatism +1.50 D plus cylinder, 180 $^{\circ}$)
- BCDVA photopic monocular (simulated astigmatism +1.50 D plus cylinder, 90 $^{\circ}$)
- BCDVA photopic monocular (simulated astigmatism +1.00 D plus cylinder, 180 $^{\circ}$)
- BCDVA photopic monocular (simulated astigmatism +1.00 D plus cylinder, 90 $^{\circ}$)
- DCIVA photopic monocular (no additional sphere, cylinder, or axis)
- DCIVA photopic monocular (simulated astigmatism +2.00 D plus cylinder, 180 $^{\circ}$)
- DCIVA photopic monocular (simulated astigmatism +2.00 D plus cylinder, 90 $^{\circ}$)
- DCIVA photopic monocular (simulated astigmatism +1.50 D plus cylinder, 180 $^{\circ}$)

- DCIVA photopic monocular (simulated astigmatism +1.50 D plus cylinder, 90°)
- DCIVA photopic monocular (simulated astigmatism +1.00 D plus cylinder, 180°)
- DCIVA photopic monocular (simulated astigmatism +1.00 D plus cylinder, 90°)
- DCNVA photopic monocular (no additional sphere, cylinder, or axis)
- DCNVA photopic monocular (simulated astigmatism +2.00 D plus cylinder, 180°)
- DCNVA photopic monocular (simulated astigmatism +2.00 D plus cylinder, 90°)
- DCNVA photopic monocular (simulated astigmatism +1.50 D plus cylinder, 180°)
- DCNVA photopic monocular (simulated astigmatism +1.50 D plus cylinder, 90°)
- DCNVA photopic monocular (simulated astigmatism +1.00 D plus cylinder, 180°)
- DCNVA photopic monocular (simulated astigmatism +1.00 D plus cylinder, 90°)

The data will be summarized using continuous statistics by treatment received for the mITT Set. The data will also be presented in a data listing.

15 Interim Analyses

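### The trial-frame sub-study swaps its against-the-rule and with-the-rule labels, and its single test order ties cylinder power and axis to test position

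*Protocol*

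**What the plan says.** Protocol Appendix B 8.0 states the aim of the procedure: "Residual astigmatism then will be optically simulated for each subject at distance / far (4 m), intermediate (66 cm), and near (40 cm) distances". The eye wears its manifest correction (the adjusted one at 66 cm and 40 cm), and a plus cylinder lens is added on top with a minus sphere of half its power. One worked example, with a minus sign before the sphere, reads "1.00 sph should be placed in the trial frame with the +2.00 cylinder". The lenses are "plus cylinder trial lenses placed at the 180° axis (i.e., simulating ATR astigmatism) and then at the 90° axis (i.e., simulating WTR astigmatism".

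The order is prescribed: "The order of trial lenses to be used with a subject will be the 2.00 D plus cylinder lens", then 1.50 D, then 1.00 D, with 180° before 90° at each power. Table 4 puts the no-cylinder test first at each distance and runs far, intermediate, near. The A eye goes first, and the B eye repeats the sequence.

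Protocol 13.5.5.4 plans two descriptive outputs: acuity for each distance, power and axis in degrees, and "The within-eye difference in logMAR VA between without astigmatic correction (0.00 D cylinder power) and with astigmatic correction", again by distance, power and axis. SAP 14.12 lists the conditions by power and axis in degrees and says only: "The data will be summarized using continuous statistics by treatment received for the mITT Set". It does not mention the within-eye difference.

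The only definition of the two orientations is in SAP 14.2, for manifest refraction converted to negative-cylinder notation. It includes "With-the-rule: 1° to 30° or 150° to 180" degrees; against-the-rule is 60° to 120°.

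**The concern.** The sub-study exists to describe how residual astigmatism affects acuity, by amount and by orientation. Appendix B 8.0 holds the only key in either document that turns its axes into ATR and WTR. If that key is backwards, a report or labelling text that speaks of ATR and WTR tolerance would say the opposite of what was observed.

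The amount question has a different weakness. Each power and axis always occupies the same place in the sequence, and the no-cylinder reference is always first. Any change in performance over the session therefore enters the contrasts that Protocol 13.5.5.4 plans. If the SAP is followed as written, the within-eye difference, which is the most direct answer to the sub-study's question, might not be produced at all.

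**Working it through.** **The plan's own figures.** Sub-study size: (30 + 15)/(1 − 0.10) = 50, as stated in Protocol 13.3.6.4. Sphere offset: spherical equivalent = S + C/2. This gives −1.00 + 2.00/2 = 0, −0.75 + 1.50/2 = 0 and −0.50 + 1.00/2 = 0, as Appendix B intends. Both reproduce.

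**Orientation.** The power of a lens in meridian m is P(m) = S + C·sin²(m − axis).

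1. Added lens −1.00/+2.00 × 180: P(90) = −1.00 + 2.00 = +1.00 D and P(180) = −1.00 D. The vertical meridian gains plus power.
2. The refraction that neutralises it reverses both signs: +1.00/−2.00 × 180. Check: its power is +1.00 − 2.00 = −1.00 D at 90 and +1.00 D at 180, so the sums with step 1 are zero.
3. This is already in negative-cylinder form with axis 180, so SAP 14.2 makes it with-the-rule. Appendix B calls it ATR.
4. Added lens −1.00/+2.00 × 90: the neutralising refraction is +1.00/−2.00 × 90, against-the-rule under SAP 14.2. Appendix B calls it WTR.
5. The 1.50 D and 1.00 D lenses give the same result, so all six power and axis combinations are opposite to their label.
6. The printed labels result only if the added lens is read as the eye's prescription: −1.00/+2.00 × 180 transposes to +1.00/−2.00 × 90, which is ATR. But that lens would correct ATR astigmatism. Worn over a full correction, it simulates the opposite.

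**Order.** Conditions per eye: 7 at each of 3 distances. Tests per subject: 7 × 3 × 2 = 42.

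| Condition | Positions within a distance | Mean position |
|---|---|---|
| 0 D | 1 | 1.0 |
| 2.00 D | 2, 3 | 2.5 |
| 1.50 D | 4, 5 | 4.5 |
| 1.00 D | 6, 7 | 6.5 |

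A model with an intercept, six condition terms and six position terms has 13 columns but rank 7, so position and condition are the same factor. A straight-line drift over all 42 tests, with eye, distance and condition in the model, has 11 columns and rank 10. It too cannot be estimated. No later analysis can separate the two.

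**Illustrative size.** Let d be the drift per test in logMAR. The documents give no value; 0.002 to 0.010, in either direction, is an assumption. The shift in a contrast is d times the difference in mean position.

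| Contrast | Position difference | Size of shift |
|---|---|---|
| 1.00 D vs 0 D | 6.5 − 1.0 = 5.5 | 0.011 to 0.055 |
| 2.00 D vs 0 D | 2.5 − 1.0 = 1.5 | 0.003 to 0.015 |
| 2.00 D vs 1.00 D | 2.5 − 6.5 = −4.0 | 0.008 to 0.040 |
| 90° vs 180° at one power | 1 | 0.002 to 0.010 |

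If performance worsens with time (d > 0), the 1.00 D effect is overstated and the gradient across powers is flattened. If it improves with practice, the reverse holds.

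**SAP against protocol.** SAP 16 lists three changes, all of them to analysis populations for safety. Dropping the within-eye difference is not among them.

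**The case against.** Most of the case on the other side concerns consequences, and much of it stands.

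- A reader might infer that the sub-study results will be reported reversed. The documents do not support that. Table 4, the study flow chart, Protocol 13.5.5.4 and SAP 14.12 all name conditions by axis in degrees, and no planned table, endpoint or hypothesis uses ATR or WTR for these conditions. The error is confined to two parentheses in one sentence.
- A reader might also take drift between far and near, or between the A and B eyes, as bias. The planned difference is taken within eye and within distance, and the no-cylinder test is repeated in each block. Under linear drift, those offsets cancel.
- It is tempting to say that the order bias equals the random error. With an assumed within-eye SD of 0.10 and 30 Test subjects, the standard error is 0.10/√30 = 0.018. At d = 0.005 the shift is 0.0075 for 2.00 D versus 0 D (0.4 standard errors) and 0.0275 for 1.00 D versus 0 D (1.5). Neither the SD nor the drift is in the documents, so no such general statement can be made. Practice and fatigue act in opposite directions, and the net drift could be near zero.
- There are mitigations. Letters are re-randomised at every use (Appendix B 2.1), which removes memorisation, and brief breaks are allowed (Appendix B 2.3), which helps against fatigue. Neither removes practice or blur adaptation.
- The sub-study is descriptive and follows Visit 5, so no primary or secondary conclusion depends on it. Both lens groups follow the same order, so a comparison between them is biased only if drift differs by lens.

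What remains: the key is wrong, the aliasing is complete, and the SAP omits a planned output without saying so.

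**Conclusion.** The two labels in Appendix B 8.0 are swapped. This is exact and needs no assumption beyond the SAP's own definition of the terms. The planned tables would be right; an ATR or WTR reading made with this key would be wrong.

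The fixed order makes the within-eye contrasts against 0 D, and the gradient across powers, inseparable from test position. That is certain from the design, but its size is unknown. The shifts of up to 0.055 logMAR (1.00 D versus 0 D) and 0.040 logMAR (2.00 versus 1.00 D) rest on an assumed linear drift of at most 0.010 logMAR per test.

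The missing within-eye difference in SAP 14.12 is an unlisted departure from Protocol 13.5.5.4. The stated purpose refers to "visual acuities in eyes implanted with the enVista trifocal toric IOLs", although the study lenses are the MX60EF trifocal and the MX60E monofocal. That is a wording slip with no effect on the analysis.

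All of this bears on what a small descriptive sub-study can conclude, not on the trial's success criteria.

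**What to change.** 1. In Appendix B 8.0, swap the labels: plus cylinder at 180° simulates WTR and at 90° simulates ATR. Cost: one sentence.
2. Replace the single sequence in Table 4 with a pre-printed schedule that counterbalances the powers and axes within each distance. The no-cylinder test must move as well; otherwise every contrast with it stays tied to first position. No tests are added for the roughly 50 subjects at up to 10 sites. The downside is more lens handling and some risk of a swap error, since each cylinder needs its matched sphere. The present order needs 3 power changes per distance. A fully random order of the seven conditions needs on average 6 − 3 × 2/7 ≈ 5.1, or about 31 against 18 over the six blocks. Keeping the two axes of a power adjacent, and varying the power order and the axis order, holds it at 3.
3. For subjects already tested at Visit 6, keep the data and state the order limitation, and record which scheme each subject followed.
4. In SAP 14.12, restore the within-eye difference from no cylinder for each distance, power and axis, or list and justify its omission in SAP 16.
5. Remove the word toric from the purpose statements in Protocol 13.3.6.4 and Appendix B 8.0 and in SAP 4.2.4 and 6.6.4.
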